#### 3.2 Number of subjects

It is planned to assess >100 subjects for eligibility and to allocate 80 subjects. Recruitment and treatment of subjects is expected to be performed in up to 100 trial centres. We expect an equal distribution between START and STOP blocks.

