### 3.5 Measures taken to minimize/avoid bias

#### 3.5.1 Randomization

Patients will be allocated to the two treatments, i.e., oral hydroxychloroquine and placebo, in a ratio of 1:1 by central randomization within each age group.

The age-matched stratification will be performed according to 2 age groups defined as infants > 3 Wks, < 2 y and the age category Children > 2 y, because of an anticipated skewed frequency distribution of cases, the older ones being less frequent.

The randomization procedure will not consider the sex of the patients, since no sex-specific responses to HCQ therapy have been reported yet and are not expected. The randomization list will be generated by an independent institute using a validated system, which involves a pseudo-random number generator to ensure that the resulting treatment sequence will be both reproducible and non-predictable.

Only patients who participate in the chILD EU register can be included in the HCQ study. Inclusion in the chILD EU register and in the HCQ study can be performed at the same day.

Patients will not receive a distinct HCQ patient number. The HCQ patient number corresponds to the respective patient number of the chILD EU register.

At screening, each patient to be included will receive the next consecutive random/ patient number from a block of randomization numbers per age group. Study medication will be packed and blinded according to the random list. Each patient medication box will be sent together with the sealed unblinding codes (i.e. envelopes) to the sites. The investigator has to take care that each patient will be provided with the study medication box bearing the correct randomization number.

The randomization list is to be kept confidential and is only accessible to authorized personnel until the code is broken. At the end of the trial, any emergency opening of the envelopes will be controlled after collecting the explanations for unblinding and checking the unused treatment units. The code will be broken regularly only at the end of the study after freezing the statistics database (by checking the data, recording any protocol violations etc.) allowing the collected data to be analyzed.

The randomization list will be kept in safe and confidential custody.

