### 8.1 Sample size

Due to the exploratory nature of the study there is no formal sample size calculation. The study aims to include 80 patients.

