#### 8.3.1 Definition and analysis of primary outcome

The oxygenation of the patient is the primary outcome variable. The primary outcome will be assessed as the response rate of oxygenation to the intervention. As the patient's respiratory condition can vary over a broad range, may necessitate variable external support, and as these changes may occur over relatively short time periods, it is necessary to take all this into consideration when assessing oxygenation. Therefore we defined the parameters to be measured depending on the patient's condition to define a responder (Table 3.8-1). The majority of children included into the study are expected to be on supplemental oxygen or in room air. In these subjects oxygen saturation in room air will be assessed (for assessments please see 3.2). However to include the broad continuum of respiratory support possible in individual patients, an approach was chosen accommodating that need. Responses to treatment judged as significant were defined depending on Patient's condition. How and when to assess the variables is further detailed in the study protocol.

Oxygenation, the primary outcome parameter, was chosen as a dichotomous variable (response yes or no). Its components, i.e. O2-saturation and respiratory rate, are also used continuously in a descriptive manner as secondary outcome variables.

Tab 3.8-1: Definition of responders to treatment depending on Patient's condition

Patient's condition	Measured parameters	Specific metric	Definition of significant change or responder to the initiation of HCQ	Definition of significant change or responder to the withdrawal of HCQ	Method of aggregation
In room air	In room air O2 Sat (mean value) Respir rate (mean value)	Change from baseline	Increase $\geq 5\%$ in O2 Sat, or Decrease in resp. rate $\geq 20\%$	Decrease $\geq 5\%$ in O2 Sat, or Increase in resp. rate $\geq 20\%$	Proportion of responders
On O2-supplement	In room air O2 Sat (mean value) Respir rate (mean value)	Change from baseline	Increase $\geq 5\%$ in O2 Sat or Decrease in resp. rate $\geq 20\%$ or Support no more needed	Decrease $\geq 5\%$ in O2 Sat, or Increase in resp. rate $\geq 20\%$ or Support newly needed	Proportion of responders
On high-flow nasal cannula	O2-flow, air-flow	Change from baseline	Decrease $\geq 20\%$ or Support no more needed	Increase $\geq 20\%$ or Support newly needed	Proportion of responders

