6.6 Primary Analysis

The variable assessing the primary outcome is the response rate measured by the oxygen saturation in room air.

START HCQ block

Relative change from trial day 1 (Visit 2) to day 28 (Visit 3) and day 56 (Visit 4) and from day 28 to day 56 change from active compound compared to change from placebo

STOP HCQ block

Relative change from trial day 1, i.e. Visit 2, through day 84, i.e. Visit 5: change from active compound compared to change from placebo

Both blocks separately

a) A difference between the changes in placebo and active phases is considered significant as described in the table below.

Patient's condition	Measured parameter	Definition of significant change or responder
Stable in room air or on	SpO2 in room air	Increase $\geq 5\%$

O2-supplement		
On high-flow nasal cannula	O2-flow, air-flow	Decrease $\geq 20\%$ or support not needed any more
Ventilated	Oxygenation index	Decrease $\geq 20\%$ or support not needed any more
On ECMO		Decrease $\geq 20\%$ or support not needed any more

The analysis will be done first by discarding the information on the patient's condition. Descriptive analyses will be done overall and for all patients conditions separately.

b) Patients are defined as responder as described in the table above. The numbers of responders are counted and compared by Fisher's exact test as well as logistic regression models with factors for treatment group and age group.

The following SAS code can be used:

```
PROC LOGISTIC DATA=indata;
  CLASS treatment age_gr;
  MODEL responder_YN = treatment age_group treatment*age_group;
RUN;
```

Both blocks together

Not applicable. There were too few patients in both blocks.

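### Neither responder test uses the baseline support condition that sets the responder rule; an exact test with a few coarse strata would use it at little cost

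*SAP*

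**What the plan says.** Protocol 8.3.1 makes the endpoint depend on condition: "Responses to treatment judged as significant were defined depending on" the patient's condition. SAP 6.6 a) carries this into its own table. Patients in room air or on supplemental oxygen respond through SpO2 in room air. High-flow, ventilated and ECMO patients respond through a fall of at least 20% or the end of support.

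SAP 6.6 a) then sets condition aside for the first analysis and adds: "Descriptive analyses will be done overall and for all patients conditions separately". SAP 6.6 b) compares responders by Fisher's "exact test as well as logistic regression models with factors for treatment group and age group". It does not say which of the two is the main test.

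Randomisation is "in a ratio of 1:1 by central randomization within each age group", with two age groups (Protocol 3.5.1). Support condition is not a stratification factor. Protocol 8.1 says: "Due to the exploratory nature of the study there is no formal sample size calculation".

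**The concern.** A factor that fixes the measure, the threshold and the route to response is likely to affect the chance of response. Pooling then has two costs.

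- **Power.** Differences between conditions enter the pooled comparison as noise, and Fisher's test is already conservative at this size.
- **Chance imbalance.** Condition is left to chance. Suppose, for illustration, control rates of 5% and 50% in two conditions, and one arm with 3 of 20 more patients in the second. With no drug effect, the expected crude responder difference in that allocation is 3/20 × (50 − 5) = 6.75 percentage points, and no planned test adjusts for it.

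Numbers are small and the disease is rare, so baseline information already collected should not be wasted.

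**Working it through.** **No planned figure to reproduce.** The documents give no response rate, effect size, alpha or power. Arm size follows from Protocol 3.2: "It is planned to assess >100 subjects for eligibility and to allocate 80 subjects", and "We expect an equal distribution between START and STOP blocks". So 80 / 2 blocks / 2 arms = 20 per arm.

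**Why condition may be prognostic.** In START, under the SAP table, a room-air patient responds only by an SpO2 rise of at least 5%. Read as a relative rise, this is impossible from a baseline above 100/1.05 = 95.2%; read as absolute, above 95%. Protocol 3.6.1 sets no SpO2 limit for entry, and Protocol 1.2 admits patients with minimal symptoms. Some room-air patients may therefore be unable to respond on either arm. The responder table in Protocol 8.3.1 also gives patients on oxygen a route, support no longer needed, that room-air patients lack. This makes differing rates plausible but does not prove them.

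**Tests compared.** In stratum s, with N_s patients, n_s on HCQ and m_s responders, the HCQ responders X_s are hypergeometric (N_s, m_s, n_s) under no effect. The statistic is T = ΣX_s, and its null distribution is the convolution of the stratum distributions. The two-sided p sums all P(T = t) no larger than P(T = observed). Pooled Fisher is the same test with one stratum.

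**Assumptions.** Alpha is 0.05, age groups are equal and balanced by design, and condition is allocated by chance. Shares and control rates are in the order room air / O2 / high-flow or ventilated. HCQ rate = OR·p/(1 − p + OR·p); for example p = 0.2 and OR 6 gives 1.2/2.0 = 0.6. Each row has 8,000 simulated trials, with Monte Carlo error on a power near 50% of √(0.25/8000) = 0.6 points.

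Power (%) at 20 per arm:

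| Shares; control rates; OR | Fisher | 3 conditions | 2 rule groups × age | 6 cells |
|---|---|---|---|---|
| 45/45/10; 20/20/20%; 6 | 65.4 | 67.5 | 67.4 | 64.8 |
| equal; 10/10/10%; 6 | 49.1 | 51.5 | 50.8 | 48.2 |
| 45/45/10; 20/20/35%; 6 | 64.1 | 67.0 | 67.0 | 64.8 |
| 45/45/10; 10/20/40%; 6 | 56.0 | 59.8 | 58.6 | 56.9 |
| 45/45/10; 5/20/50%; 6 | 44.5 | 51.8 | 48.6 | 49.6 |
| 45/40/15; 5/30/50%; 8 | 54.1 | 66.5 | 60.1 | 63.6 |
| 30/50/20; 5/30/50%; 8 | 58.5 | 71.9 | 65.6 | 69.4 |
| equal; 5/20/50%; 6 | 40.8 | 54.0 | 51.2 | 50.6 |
| 45/40/15; 0/20/40%; 12 | 42.0 | 61.5 | 46.7 | 57.3 |
| No effect: 45/40/15; 5/30/50%; 1 | 2.0 | 2.7 | 2.5 | 2.6 |

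**Gains at 20 per arm.** With flat rates both coarse versions gain about 2 points; a separate four-cell run with a flat 20% rate gave 65.5% to 66.4%. With moderate to strong differences they gain from 58.6 − 56.0 = 2.6 to 71.9 − 58.5 = 13.4. When room-air patients cannot respond, three conditions gain 61.5 − 42.0 = 19.5. The rule-group version gains only 46.7 − 42.0 = 4.7 there, because it merges room air with O2.

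**At 12 per arm**, standing in for missing values or low recruitment, both coarse versions gained about 1 to 12 points in the same scenarios, with no loss. Six cells lost up to 4 points (39.3% to 34.9% with control rates 20/20/35%).

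**Effect confined to the majority.** With an 80/20 split by condition, a 20% control rate in both groups and an effect (60%) only in the larger group, power still rises from 45.8% to 51.6%.

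**The case against.** The trial is exploratory, and Fisher's test is valid. The SAP already adds a logistic model with age group and descriptive results by condition. On this view, exchanging one valid conservative test for another is a preference. Protocol 8.3.1 also expects most patients in room air or on oxygen, which share one rule in the SAP, so strata for higher support would be nearly empty.

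Much of this stands. The planned tests are valid, age is handled by the logistic model, and sparse cells do defeat the six-cell split when numbers fall. What does not stand is that the logistic model covers the gap, because it has no support term. As coded it also adds a treatment-by-age interaction that the text omits. In simulations with age-group control rates 20/20%, 30/10% and 50/10%, Wald power was 73.3%, 67.3% and 57.0% without that term. With it, power was 54.5%, 33.3% and 22.4%, counting fits with an empty or full cell as non-significant. That is a separate and larger defect in the same section.

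Stronger readings that the documents do not support:

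- **That the pooled comparison is biased.** Condition is randomised by chance, so imbalance averages to zero and adds noise, not bias.
- **That a large power loss is established.** Two equal strata, balanced between arms, with rates (placebo/HCQ) 5/30% and 50/90% give 38.6% against 60.1%. That rests on assumed rates and an even split, and sits poorly with the expected patient mix.
- **That the protocol names only Fisher's test or ignores age.** Its synopsis also names logistic regression for the combined analysis, and it allows age adjustment where appropriate.

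**Conclusion.** The point holds as a gap in precision and interpretation, not an error of validity. The outcome rule depends on condition, condition is recorded, and no planned responder test uses it.

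At 20 per arm the coarse stratified test costs nothing in the scenarios run. It gains about 1 to 3 points if condition does not matter, about 3 to 13 if it matters moderately to strongly, and up to about 19 if one condition cannot respond. All of this rests on assumed rates, shares, odds ratios and alpha, so only the direction and rough range should be relied on. Nothing here changes type I error, which stayed below 3% for every version in the no-effect run.

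**What to change.** In SAP 6.6 b), before unblinding:

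- Name the main responder comparison as an exact stratified test, with the exact common odds ratio and its confidence interval: `PROC FREQ; TABLES stratum*treatment*responder / CMH; EXACT COMOR;`.
- Choose one stratum definition from Visit 2 data. Either use condition in three levels (room air / O2 supplement / high-flow or ventilated, stating where ECMO falls), or two rule groups (room air or O2 supplement / high-flow, ventilated or ECMO) crossed with age group. The first recovers more if room-air patients cannot respond; the second keeps the randomisation factor.
- Do not cross three conditions with age unless numbers allow.
- Keep pooled Fisher as a supporting result.

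The cost is a few lines of SAP text and one SAS step on data already collected. Strata with patients in one arm only, or with no or all responders, add no information. A common odds ratio also summarises an effect that may differ between strata, so the descriptive results by condition should stay.

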### 8.2 Analysis populations

All subjects with signed informed consent are considered as enrolled subjects, even if they did not receive any trial treatment. All randomised subjects will be included in the Intention-to-treat (ITT) population. This population is the primary analysis population. Within ITT population analyses subjects will be assigned to the treatment to which they were randomised. For the combined analysis the ITT Population consists of all patients that are at least in the START or the STOP block. The corresponding PP Populations consist of the patients from the ITT population without major protocol violations. Major protocol violations will be defined in the SAP. The safety population comprises all subjects who received at least one dose of trial treatment. In analyses of the safety population subjects will be assigned to the treatment which they actually received. The analysis populations will be defined prior to unblinding of the study.

For analysis, subgroups of patients will be defined, based on age, categories of diagnosis and further appropriate factors.

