### 8.3 Efficacy analyses

The primary population for the analyses of efficacy are the ITT Populations (randomised patients) for each block. For the combined analysis the ITT Population consists of all patients that are at least in the START or the STOP block. For all hypotheses two-sided exploratory p-values will be provided.

If appropriate, the analyses will be adjusted for the stratification factor of the randomization: age group. The final efficacy analysis will be described in the Statistical Analysis Plan (SAP).

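### The sample code for the age-adjusted responder model adds a treatment-by-age interaction that no text describes, and names the age variable two ways

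*SAP*

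**What the plan says.** SAP 6.6 b) compares responder counts in each block by Fisher's exact test and by "logistic regression models with factors for treatment group and age group". Code follows, introduced by "The following SAS code can be used". Its two relevant statements are "CLASS treatment age_gr" and "MODEL responder_YN = treatment age_group treatment*age_group".

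Protocol 8.3 foresees adjustment only: "If appropriate, the analyses will be adjusted for the stratification factor of the randomization: age group". The synopsis says the same. Protocol 8.2 does anticipate age subgroups: "For analysis, subgroups of patients will be defined, based on age, categories of diagnosis and further appropriate factors". SAP 6.8, however, marks subgroup analyses as not applicable. Neither document defines `age_gr` or `age_group`.

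**The concern.** The logistic model is the only analysis in SAP 6.6 that uses the factor by which randomisation was stratified. The prose names two factors, while the code adds their product. With two arms and two age groups the coded model has four parameters for four cells. Its treatment coefficient is then no longer a common age-adjusted log odds ratio. Under the default effect coding of PROC LOGISTIC it is the equal-weight average of the two stratum-specific log odds ratios, and it exists only if both of those are finite.

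An analyst who follows the prose and one who follows the code can therefore report different age-adjusted results from the same data, or one of them may have no usable result. The two variable names add a second fault, because `age_group` is not declared as a classification variable.

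**Working it through.** **What the printed code does.** There are three cases:

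- The data set holds only `age_gr`: the step stops with an error.
- `age_group` exists as a character variable: it also stops, because the variable is not in CLASS.
- Both variables exist and `age_group` is numeric: the step runs, but the treatment coefficient refers to `age_group` = 0.

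**Inputs for the sparse-cell check.** The documents give no figure to reproduce, since Protocol 8.1 has no formal sample size calculation.

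- 80 patients (Protocol 8.1), split equally between START and STOP (Protocol 3.2), allocated "in a ratio of 1:1 by central randomization within each age group" (Protocol 3.5.1). This gives 80 / 2 / 2 = 20 per arm per block.
- Two age groups (Protocol 3.5.1).
- Assumed, not documented: age splits per arm of 10/10, 13/7 and 16/4, and the response rates in the table, equal across age groups. Protocol 3.5.1 anticipates a skewed age distribution, so 10/10 is the favourable end.

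**Formulas.** A cell of size n with response rate p contains both responders and non-responders with probability 1 − (1−p)^n − p^n.

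- Coded model, name corrected: the treatment term is finite only if all four cells are mixed, so P(no finite estimate) = 1 − the product of the four cell probabilities.
- Additive model: all 81 patterns of empty, mixed and full cells were enumerated and each checked for separation. For the treatment term, almost all the probability comes from an arm with no responders or only responders.

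**One case by hand** (0.10 v 0.30, split 10/10).

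- Placebo cell: 1 − 0.9^10 − 0.1^10 = 0.651. Active cell: 1 − 0.7^10 − 0.3^10 = 0.972.
- Coded model: 1 − (0.651 × 0.972)^2 = 0.60.
- Additive model, treatment term: an empty placebo arm has probability 0.9^20 = 0.1216 and an empty active arm 0.7^20 = 0.0008, together 0.12.

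**Results.** Probability of no finite estimate. Ranges run over the three age splits.

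| Placebo v active rate | Coded model, treatment term | Additive, treatment term | Additive, any parameter |
|---|---|---|---|
| 0.10 v 0.30 | 60%–79% | 12% | 13%–25% |
| 0.20 v 0.50 | 21%–50% | 1% | 1%–4% |
| 0.30 v 0.60 | 7%–37% | 0.1% | 0.1%–0.8% |
| 0.10 v 0.10 | 82%–92% | 23% | 33%–52% |
| 0.20 v 0.20 | 37%–67% | 2% | 4%–18% |
| 0.30 v 0.30 | 11%–44% | 0.2% | 0.3%–6% |
| 0.05 v 0.05 | 97%–99% | 59% | 70%–80% |

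**When both models converge** (invented counts).

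- Skewed table: 15 younger and 5 older per arm; responders 2 and 1 on placebo, 8 and 1 on HCQ. Stratum log odds ratios are ln[(8/7)/(2/13)] = 2.005 and ln[(1/4)/(1/4)] = 0, with average 1.003. The coded model gives odds ratio 2.73 (p = 0.273). The additive model gives 4.77 (p = 0.045).
- Balanced table: 10 and 10 per arm; responders 2 and 3 on placebo, 5 and 6 on HCQ. The coded model gives 3.74 and the additive model 3.73, each with standard error 0.69 on the log scale.
- The same balanced table with an undeclared numeric `age_group`: odds ratio 4.00 (standard error 1.01) if coded 0/1, and 4.57 (2.23) if coded 1/2.

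**The case against.** The prose names the factors without saying main effects only, so it does not strictly exclude an interaction, and Protocol 8.2 shows that age subgroups were in mind. This stands in part: the interaction may have been intended. It is still described nowhere, and SAP 6.8 points the other way.

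The variable name is probably a typing slip that would surface at run time. That is fair, since nothing suggests both variables exist. The odds ratios 4.00 and 4.57 apply only in that special case.

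The probabilities rest wholly on assumed rates. At lower rates both models separate: at 0.05 in both arms the additive treatment term already fails 59% of the time, so dropping the interaction does not reliably rescue the estimate. This also stands, and it is the argument for a penalised fit.

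Finally, the consequence is bounded. The code is offered rather than required, adjustment is conditional, Fisher's exact test does not depend on it, separation usually shows as a convergence warning or very large standard errors, and Protocol 8.3 states "For all hypotheses two-sided exploratory p-values will be provided". These limits keep the point at the level of a recommended correction. They do not settle which model the SAP means.

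**Conclusion.** The concern holds. Prose and code in SAP 6.6 b) do not specify the same model, and the code as printed does not deliver the age-adjusted comparison described. This part rests on the documents alone.

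The size depends on assumptions: 20 per arm per block, the three age splits, and response rates equal across age groups. In every scenario examined, the coded model leaves the treatment term without a finite estimate more often than the additive model. For rates from 0.10 upwards the ranges are 7% to 92% against 0.1% to 23%. When both models converge, the difference between them depends on the data, from negligible in a balanced table to substantial in a skewed one. This is a recommended correction to an exploratory analysis; the unadjusted comparison is not affected.

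**What to change.** In SAP 6.6, use one age variable name in both CLASS and MODEL, and fit main effects of treatment and age group only as the age-adjusted model. If effect modification by age is wanted, describe it in the text as a separate exploratory model and say which treatment contrast it reports.

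As an optional addition, specify Firth penalisation with profile-likelihood limits, because the additive model can also separate at low response rates.

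The cost is one variable name and one model term, with no new data. With the Firth option, estimates are slightly shrunken.
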